## Patient Reported Outcome Measures (PROMS)

Three PROMS: PROMIS, FAOS and AOS are measured prior to surgery and at very post-surgery visit. Descriptive summaries and confidence intervals at each visit will be presented. In addition, improvement from baseline in PROMS score will also be presented descriptively.

### **PROMIS Global Health**

The Patient-Reported Outcomes Measurement Information System (PROMIS®) is a National Institutes of Health initiative to develop state-of-the-science measures that assess function and wellbeing in the physical, mental and social domains of health. PROMIS® have two components: physical and mental health. Scoring the PROMIS will be based on the PROMIS Global Health Scoring guidance (PROMIS® Global Health Scoring Manual).

## Foot and Ankle Outcome Score (FAOS)

FAOS is a self-report measure that evaluates symptoms and functional limitations in individuals with generalized foot and ankle disorders. Items for the FAOS were adapted from the Knee Injury and Osteoarthritis Outcome Score. The FAOS is composed of the

Page 14 of 23

following 5 subscales: pain (9 items), other symptoms (7 items), activities of daily living (7 items), sports and recreational activities (5 items), and foot and ankle-related quality of life (4 items). Each of the FAOS subscale are standardized so that score ranges from 0 to 100, where 100 indicates no problems and 0 indicates extreme problems.

### Ankle Osteoarthritis Score (AOS)

The AOS consist of 2 components: Pain and Disability, with 9 questions each, are used to calculate the Total AOS score. The score is from zero to one hundred with a lower score indicating more normal function

### **Radiographic Assessment**

Pre-operative radiograph assessment will be summarized based on the COFAS scale and by the degree of varus and/or valgus deformity. Post-operatively, at 6 months, one, two, five, seven, and ten years follow-up visits, radiographic findings implant component migration, loosening, subsidence and issues of osteolysis, cyst and other relevant radiographic findings will be summarized as rates and frequencies for all subjects and by subgroups. At the end of the study, the overall rates of these radiographic findings will also be summarized.

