#### Overview

Procedural and device related events will be described and collected on the AE form. It is the responsibility of the operating surgeon/s to be aware and note the adverse effects from the package insert/instructions for use by the manufacturer/sponsor. (See appendix A) The number of subjects experiencing each adverse event percentage or proportion of the total number of subjects experiencing each adverse event will also be reported. All adverse events shall be reported in an interim and/or final report of the clinical investigation. All device deficiencies related to the identity, quality, durability, reliability, safety or performance of the investigational medical device shall be documented throughout the clinical investigation and appropriately managed by the sponsor.

Potential intraoperative and early postoperative complications, related to all total ankle replacements may include:

- pain;
- sudden drop in blood pressure intra-operatively due to the use of bone cement;
- damage to blood vessels;

- temporary or permanent nerve damage resulting in pain or numbness of the affected limb;
- cardiovascular disorders including venous thrombosis, pulmonary embolism, or myocardial infarction.
- hematoma;
- delayed wound healing; and
- deep wound infection (early or late) which may necessitate removal of the prosthesis.
- rarely an arthrodesis of the involved joint or amputation of the limb may be required.

Potential, late postoperative complications can include:

- pain;
- bone fracture by trauma or excessive loading, particularly in the presence of poor bone stock;
- peri-articular calcification or ossification, with or without impediment to joint mobility; and
- inadequate range of motion due to improper selection or positioning of components or peri-articular calcification.

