### SAFETY ANALYSIS AND REPORTING

All safety analyses will be performed on all subjects enrolled and implanted with any TAR. Adverse events and other safety evaluations will be reported as frequency and rates as appropriate, cumulative over the different follow-up schedules. In addition to all patients, subgroup summaries ( "standard instrumentation" and "approved additional instrumentation"), COFAS type, etc. will be presented. Adverse events and other safety evaluations will be reported as frequency and rates as appropriate, cumulative over the different follow-up schedules to each of the aforementioned surgical techniques.

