### **Missing Data**

Missing data will not be imputed. Patients who were missing data required for a given analysis will be excluded.

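### Ten-year adverse-event and radiographic rates are planned with no allowance for incomplete follow-up, and the overall radiographic rate has no defined denominator

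*SAP*

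**What the plan says.** **Radiographic findings.** Under Radiographic Assessment in the SAP, migration, loosening, subsidence, osteolysis, cysts and other findings at each post-operative visit "will be summarized as rates and frequencies for all subjects and by subgroups". The section then adds: "At the end of the study, the overall rates of these radiographic findings will also be summarized". It defines no numerator, denominator or treatment of subjects who stop attending.

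**Adverse events.** The SAP section Safety Analysis and Reporting fixes the population: "All safety analyses will be performed on all subjects enrolled and implanted with any TAR". Events "will be reported as frequency and rates as appropriate, cumulative over the different follow-up schedules". The Protocol's Adverse Events overview, in a sentence that is not fully grammatical, says the "percentage or proportion of the total number of subjects experiencing each adverse event will also be reported". The SAP's General Considerations present categorical data as counts and percentages.

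**Incomplete follow-up.** The Protocol section on study duration recognises the risk of loss over so long a study but does not quantify it. Its Device Failure section withdraws subjects once a tibial or talar metal component is removed. The SAP's Missing Data section allows no imputation and adds: "Patients who were missing data required for a given analysis will be excluded".

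**Contrast.** For device survivorship, the SAP specifies Kaplan-Meier and life-table analysis with censoring at last follow-up. For satisfaction, it names the denominator as the patients who report. The radiographic and adverse-event sections do neither.

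**The concern.** A proportion of everyone implanted counts a subject lost at year 3 as if observed without the event to year 10. For early complications this matters little. For loosening, subsidence, osteolysis and cysts it can matter more: the SAP's safety objectives name these as complications of interest, and late cases would fall in years when fewer subjects are still being filmed. The Protocol also lets patient-reported outcomes be completed remotely, so missing films may exceed loss of contact.

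Two things are at stake. One is the level of the 10-year safety figure that would be quoted for the device. The other is the subgroup summaries by instrumentation and COFAS type: groups with the same true risk but different loss would show different proportions. For radiographs, the open denominator also means the choice could be made after the data are seen.

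**Working it through.** The documents give no adverse-event rate, radiographic rate or loss rate, so there is no planned figure to reproduce. The check asks what each reading of the text would return for a known truth.

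**Inputs.** N = 155 implanted and visits at 6 months and 1, 2, 5, 7 and 10 years are from the SAP. True 10-year incidence F = 20% and loss by 10 years L = 10% to 50% are assumptions. Loss is random and hazards are constant unless stated.

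**Step 1: all implanted as denominator, events seen when they occur.** Let λ = −ln(1−F)/10 and μ = −ln(1−L)/10. The expected proportion is λ/(λ+μ) × [1 − exp(−10(λ+μ))].

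For F = 20% and L = 30%: λ = 0.0223, μ = 0.0357, and exp(−10(λ+μ)) = 0.8 × 0.7 = 0.56. The proportion is (0.0223/0.0580) × 0.44 = 16.9%.

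| Loss by 10 y | Reported rate (true 20%) | Subjects of 155 (true 31.0) | Relative shortfall |
|---|---|---|---|
| 10% | 19.0% | 29.5 | 5% |
| 20% | 18.0% | 27.9 | 10% |
| 30% | 16.9% | 26.2 | 15% |
| 50% | 14.6% | 22.6 | 27% |

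The relative shortfall is nearly the same for other incidences. At 30% loss, a true 10% becomes 8.4% and a true 30% becomes 25.5%. Two subgroups that share a true 20% but lose 10% and 30% would show 19.0% and 16.9%.

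**Step 2: film findings, detected only at scheduled visits.** This was simulated with 1,000,000 subjects, F = 20% and L = 30%, under the denominators that the radiographic text leaves open.

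| Denominator | Rate | Direction |
|---|---|---|
| All implanted | 16.3% | down |
| Any post-operative film | 16.5% | down |
| 10-year attenders, ever found, random loss | 20.0% | none |
| 10-year attenders, if half of those with a finding leave after detection (assumed) | 13.8% | down |
| All findings counted, event-free subjects with incomplete follow-up dropped | 22.5% | up |

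The last row is one reading of the Missing Data rule. Findings detected are 0.1625 of all subjects, and event-free subjects followed to 10 years are 0.8 × 0.7 = 0.56, so 0.1625/(0.1625 + 0.56) = 22.5%. At 20% and 40% loss the same reading gives 21.5% and 23.7%, against 17.5% and 14.9% for all implanted. If onset is late (Weibull shape 2, assumed), the all-implanted figure at 30% loss falls to 15.2%.

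**Step 3: a censoring-aware estimate.** Kaplan-Meier over the visit grid, in the same simulations with random loss of 20% to 40%, returned 19.96% to 20.08% for a true 20%.

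**The case against.** The strongest reply is that crude proportions are an inference for radiographs. The SAP says only rates, and the Protocol sentence about the total number of subjects concerns adverse events. This stands. A reader might infer that the overall radiographic rate is certain to be understated, or that the implant must look safer as attrition grows. The documents do not support either, because the denominator is undefined and the Missing Data rule permits readings that give no bias or an upward one.

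A reader might also infer that deaths and component removals bias the proportion in the same way as loss. They do not. A competing-risk estimate also keeps such subjects in the population without the event, and with no censoring it equals the simple proportion. The Protocol also has removals recorded on the adverse event form. The bias comes from subjects whose later history is unobserved. Nor do the documents say why Kaplan-Meier was chosen for survivorship, so no motive should be read into its absence here.

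The plan does give partial protection. Radiographic findings and adverse events are tabulated by visit (Tables 3.1 and 4.3). Retention, deaths and data completeness are accounted for at follow-up. Failures leading to surgery already enter the survivorship analysis. These make attrition visible, but they do not yield a 10-year cumulative incidence for findings or events that do not lead to surgery.

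Finally, no hypothesis or decision rule rests on these rates, and at 10% to 20% loss the shortfall is only about 1.5 to 3 subjects of 155. That limits the severity and does not remove the point.

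**Conclusion.** The point holds in this form. Adverse-event rates, read from the Protocol and SAP together, are cumulative proportions of all implanted subjects, and under random loss these understate 10-year incidence. The overall radiographic rate is undefined: from one truth of 20% with 30% loss, the readings examined run from 13.8% to 22.5% under constant hazards, so its direction of bias cannot be stated.

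The all-implanted shortfall is about 5% in relative terms at 10% loss, 15% at 30% and 27% at 50%. These sizes rest on assumed incidence, loss, constant hazards and random loss. The 13.8% figure also assumes that half of those with a finding leave after detection. None of these values can be taken from the documents. The primary endpoint is unaffected. This is a worthwhile, inexpensive improvement to the safety reporting.

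**What to change.** Amend the SAP sections Radiographic Assessment and Safety Analysis and Reporting as follows.

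- For each radiographic finding, and for device- or procedure-related adverse events, report time to first occurrence as cumulative incidence with 95% CI and number at risk at 2, 5, 7 and 10 years.
- Censor at last film for radiographic findings and at last contact for adverse events.
- Treat death and component removal as competing events, except where removal is itself the event. Treating them as censoring would overstate incidence.
- Make this the headline cumulative rate, with the crude count and its denominator beside it.
- Base by-visit radiographic percentages on subjects with a film at that visit.
- Films are two to three years apart after year 2, so analyse film findings as interval-censored or as life-table estimates on the visit grid.

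The cost is a few extra tables from data already held. Late rates will be less precise and, compared with a proportion of all implanted, somewhat less favourable.

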### **TAR Satisfaction**

At each post-operative visit, the patient satisfaction of their total ankle replacement will be summarized by frequency and percent for each satisfaction category. Rates will be calculated based on the number of patients reporting.

### Planned visits and Follow-Up Time Points

Subjects will be seen prospectively at the following intervals Pre-Op, Operative, 6 months, 1, 2, 5, 7, and 10 years. There are special circumstances where subjects required a visit outside the windows of the established visits, data collected from unscheduled visits will be included and analyzed. Data from an unscheduled visit maybe used to an adjacent missed visit.

### SAFETY ANALYSIS AND REPORTING

All safety analyses will be performed on all subjects enrolled and implanted with any TAR. Adverse events and other safety evaluations will be reported as frequency and rates as appropriate, cumulative over the different follow-up schedules. In addition to all patients, subgroup summaries ( "standard instrumentation" and "approved additional instrumentation"), COFAS type, etc. will be presented. Adverse events and other safety evaluations will be reported as frequency and rates as appropriate, cumulative over the different follow-up schedules to each of the aforementioned surgical techniques.

#### 1. Adverse Evets

Adverse Event (AE) is defined as any untoward medical occurrence, unintended disease or injury, or untoward clinical signs (including abnormal laboratory findings) in subjects, users, or other persons, whether or not related to the investigational medical device. All adverse events shall be reported in an interim and/or final report of the clinical investigation. Frequency of these complications will be summarized by according to Preferred Term (PT) and System Organ Class (SOC) using Medical Dictionary for Regulatory Affairs (MedDRA 18.0).

The Investigator will follow up subjects who experience an AE until it is either resolved, determined to be chronic, stable, or, until the subject's participation in the study ends. Prior to completion of the study, the Investigator will complete the Adverse Event Status Update Case Report Form to document any AE's previously reported as ongoing.

Intra-operative and post-operative complications, whether device-related or not, suspected or not complications will be reported as adverse events. Potential intraoperative and early postoperative complications, related to all total ankle replacements may include:

- a. pain;
- b. sudden drop in blood pressure intra-operatively due to the use of bone cement;
- c. damage to blood vessels;
- d. temporary or permanent nerve damage resulting in pain or numbness of the affected limb;

e. cardiovascular disorders including venous thrombosis, pulmonary embolism, or myocardial infarction.

f. hematoma;

- g. delayed wound healing; and
- h. deep wound infection (early or late) which may necessitate removal of the prosthesis.
- i. rarely an arthrodesis of the involved joint or amputation of the limb may be required.

Potential, late postoperative complications can include:

a. pain;

b. bone fracture by trauma or excessive loading, particularly in the presence of poor bone stock;c. peri-articular calcification or ossification, with or without impediment to joint mobility; andd. inadequate range of motion due to improper selection or positioning of components or periarticular calcification.

Additionally, these complications will be further categorized and reported as device related, or procedure related and outcome.

#### 1. Serious Adverse Events (SAE)

A separate summary table of complications that met the serious adverse events (SAE) classification will be presented. Serious adverse events (SAE) as defined from ISO 14155:2011(E) Clinical Investigations of Medical Devices for Human Subjects – Good clinical practice, are any adverse events that:

a. Led to death;

b. Led to serious deterioration in the health of the subject, that either resulted in

- c. A life-threatening illness or injury, or
- d. A permanent impairment of a body structure or a body function, or

e. In-patient or prolonged hospitalization, or

f. Medical or surgical intervention to prevent life-threatening illness or injury or permanent impairment to a body structure or a body function

#### 2. Subsequent secondary surgical interventions

Adverse events that lead to secondary surgical intervention will be summarized, categorized by type of surgical intervention performed, namely: reoperation, reoperation with removal of implanted components, other interventions. The primary reason for the surgical intervention will be categorized as: implant failure, deep infection, aseptic loosening, subsidence, wound healing

Page 17 of 23

problems, bone fracture, non-union and other reasons will also be tabulated in the same manner.

### **Other considerations**

### 1. Outcome Measures Report Timing

All analyses of outcome, except survivorship, will be done at each post-surgery visit namely: at 6 months, 1, 2, 3, 5, 7 years. The final analysis at 10 years will be done after all the subjects have completed final visit. In addition, at time points determined by the investigators and/or Wright Medical will be evaluated as needed or required for additional analysis of data for reporting and/or publication purposes will be done throughout the study.

### 2. Report Timing of survivorship assessment

There will be two timepoints to assess and report survivorship, at the 5th (intermediate survivorship assessment) and 10th (long-term survivorship assessment) year follow-up.

At the intermediate assessment of survivorship (5th year follow-up), only patients with follow-up scores obtained at least four years after surgery will be included in the analysis. Patients who underwent reoperation or revision surgery with in four years of surgery will not be excluded. At the final assessment of survivorship (10th year follow-up), only patients with follow-up scores obtained at least eight years after surgery will be included in the analysis. Patients who underwent reoperation or revision surgery will be included in the analysis. Patients who underwent reoperation or revision surgery will be included in the analysis.

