## Planned visits and Follow-Up Time Points

Subjects will be seen prospectively at the following intervals Pre-Op, Operative, 6 months, 1, 2, 5, 7, and 10 years. If there are special circumstances where the subjects require a visit outside the windows of the established visits, the investigator may seek approval from Wright Medical for an acceptance of an" unscheduled visit" and it will be determined if the data will be included and analyzed.

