## **Device** Failure

Subjects will be considered a treatment failure, and will be withdrawn from the study if any sections of the device (tibial or talar metal components) have been removed at any time during their participation. This should be reported onto the adverse event form. In addition, any surgical intervention during study participation that relates to their total ankle replacement will be reported on the surgical intervention case report form.

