### Survivorship of INFINITY® Total Ankle System

Survivorship of INFINITY® Total Ankle System will be based on secondary surgical intervention performed on the original implant. The Kaplan Meier survivorship method and life table analysis will be employed. Time to surgical intervention due to implant failure will be the survivorship endpoint of INFINITY® Total Ankle System. In addition, time to reoperation to exchange or remove any part of the INFINITY® Total Ankle System or surgical intervention due to failure of the implant as survivorship endpoint will also be analyzed. Subjects who did not undergo revision or reoperation due to implant failure at the time of reporting will be censored at the last follow-up. The Kaplan Meier survival curve with the 95% Confidence Interval will be constructed.

Year since	Number	Number of	Lost	Survival	95%
implantation	at start	failed implant		Rate	Confidence
					Interval
0-1	1		I		
1-2					
2-3					
3-4					
4-5					
5-6					
6-7					
7-8					
8-9					
9-10					

Table . Kaplan-Meier life-table survival of INFINITY® Total Ankle System.

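### Read literally, the SAP's 5-year survivorship set omits most metal-component removals between year 4 and the 5-year visit; this raises the estimate, while the same entry rule lowers it by dropping event-free patients

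*SAP*

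**What the plan says.** The SAP, under Report Timing of survivorship assessment, plans an intermediate report at 5 years and a final one at 10 years. For the 5-year report, "only patients with follow-up scores obtained at least four years after surgery will be included in the analysis". One exemption follows: "Patients who underwent reoperation or revision surgery with in four years of surgery will not be excluded". For the 10-year report the score must be at eight years or later, but the exemption has no time limit: "Patients who underwent reoperation or revision surgery will be included in the analysis".

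Three other provisions decide who can have a score after year 4:

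- The protocol's visit schedule reads: "Subjects will be seen prospectively at the following intervals Pre-Op, Operative, 6 months, 1, 2, 5, 7, and 10 years" (section Planned visits and Follow-Up Time Points). The 5-year visit has a window of 60 days either side.
- Protocol, Device Failure: a subject "will be withdrawn from the study if any sections of the device (tibial or talar metal components) have been removed".
- SAP, Planned visits and Follow-Up Time Points: "data collected from unscheduled visits will be included and analyzed".

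Elsewhere the SAP describes a different analysis. General Considerations takes in every enrolled subject implanted with a listed configuration. The survivorship section says "Time to surgical intervention due to implant failure will be the survivorship endpoint" and, for those without an event, "Subjects who did not undergo revision or reoperation due to implant failure at the time of reporting will be censored at the last follow-up".

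**The concern.** An exemption for reoperated and revised patients exists so that failures are not lost through lacking a late score. At 5 years it stops at year 4, one year before the time point being reported. A device removed at 4.5 years is a treatment failure under the protocol and is recorded on its adverse event form. Yet the patient's last scheduled score is from year 2, and withdrawal means that no 5-year score follows. Such a patient satisfies neither the score rule nor the exemption.

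The 5-year figure is the study's first planned survivorship report. If failures in its last year are left out by rule, that part of the curve rests on an incomplete event count, and the omission by itself works in the device's favour.

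**Working it through.** **Who enters the 5-year set.** The 2-year window closes at 2 + 60/365.25 = 2.16 years, and the 5-year window opens at 5 − 60/365.25 = 4.84 years. No scheduled score falls between them.

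| Patient | Score at 4 years or later? | Exempt? | In the set? |
|---|---|---|---|
| Metal removal at 3 years | No | Yes | Yes |
| Metal removal at 4.5 years, no unscheduled score after year 4 | No | No | **No** |
| Metal removal at 4.5 years, unscheduled score at 4.2 years | Yes | No | Yes |
| Insert exchange at 4.5 years, attends 5-year visit | Yes | No | Yes |
| Event-free, last seen at 2 years | No | No | **No** |

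The second and last rows are the two groups omitted. They push the estimate in opposite directions.

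**Inputs.** N = 155 comes from the SAP (Study Design, Overview). The documents state no survivorship rate, failure rate or loss rate, so there is no planned figure to reproduce. Failure and loss rates below are assumptions: constant hazards, independent of each other.

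**Step 1: the late failures alone.** Assume no loss, every failure a metal removal, and no unscheduled scores. With failure rate h per year:

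- failures in years 4 to 5 (dropped) = 155 × (exp(−4h) − exp(−5h))
- failures before year 4 (kept), F4 = 155 × (1 − exp(−4h))
- event-free at 5 years, R = 155 × exp(−5h)

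Nobody in the set is censored before year 5, so Kaplan-Meier at 5 years reduces to R/(R + F4). The true value is exp(−5h).

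| h per year | Failures by year 5 | Dropped | True | As written | Difference (points) |
|---|---|---|---|---|---|
| 1% | 7.6 | 1.5 | 0.951 | 0.960 | +0.9 |
| 1.5% | 11.2 | 2.2 | 0.928 | 0.941 | +1.3 |
| 3% | 21.6 | 4.1 | 0.861 | 0.884 | +2.3 |

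At 1.5%: 155 × (exp(−0.06) − exp(−0.075)) = 155 × (0.9418 − 0.9277) = 2.2 dropped; 143.8/(143.8 + 9.0) = 0.941.

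**Step 2: add loss to follow-up.** Let d be the proportion lost by 5 years, m = −ln(1 − d)/5, h = −ln(0.90)/5 and t = h + m. Then F4 = 155 × (h/t) × (1 − exp(−4t)), F45 (failures in years 4 to 5) = 155 × (h/t) × (exp(−4t) − exp(−5t)), and R = 155 × exp(−5t). True survivorship is 0.90 throughout; bracketed figures are bias in points.

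| d | F4 | F45 | R | As written, R/(R + F4) | Late failures restored, score rule kept, R/(R + F4 + F45) |
|---|---|---|---|---|---|
| 0% | 12.5 | 3.0 | 139.5 | 0.918 (+1.8) | 0.900 (0.0) |
| 20% | 11.5 | 2.4 | 111.6 | 0.907 (+0.7) | 0.889 (−1.1) |
| 30% | 10.9 | 2.2 | 97.7 | 0.899 (−0.1) | 0.882 (−1.8) |
| 40% | 10.3 | 1.9 | 83.7 | 0.890 (−1.0) | 0.873 (−2.7) |

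The net bias is zero at about 30%, 29% and 29% five-year loss for true values of 0.95, 0.90 and 0.85. If half of the year 4 to 5 failures keep a qualifying score, it is zero at about 16% to 17%.

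**Step 3: the SAP's own alternative.** Kaplan-Meier on all 155 with censoring at last follow-up was simulated at true 0.90 (2,000 runs per setting). It averaged 0.900 at 0% loss and 0.899 at 20% and 40%. The estimate as written exceeded it in 96%, 68% and 24% of runs respectively.

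**The case against.** Several counter-arguments have force.

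- **Late reoperations are not all excluded.** The protocol withdraws subjects only for removal of a metal component. A patient whose insert is exchanged after year 4 stays in the study and can supply a 5-year score, and the SAP uses unscheduled data. This stands: the gap mainly concerns metal removals. Unscheduled visits need sponsor approval under the protocol and are meant for special circumstances, so they cannot be relied on to close it.
- **The size is near a maximum.** Step 1 assumes that every failure is a metal removal, with no unscheduled scores and no loss. This stands. Fewer failures in year 4 to 5 than a constant hazard implies would shrink it further.
- **The limit may be a drafting slip,** since the 10-year exemption has none. That is plausible, but the text would be programmed as it reads.
- **The two omissions offset each other.** They do in part. Even so, at true 0.90 restoring the late failures lowers the estimate by about 1.7 to 1.8 points at every loss level in the table, so their omission always acts upward. Cancellation at one unknown loss rate does not justify either omission.

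A reader might infer that the reported 5-year survivorship will be too high overall, or that the primary endpoint is biased by this limit. The documents support neither. The net sign turns on a loss rate they do not give. The primary endpoint is survivorship at 10 years, where reoperated and revised patients are included without a time limit, so failures in year 4 to 5 are counted there.

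**Conclusion.** The 5-year rule is wrong as written. Combined with the visit schedule and withdrawal at metal removal, it normally omits recorded metal-component removals between year 4 and the 5-year visit. That omission alone raises 5-year survivorship by at most about 0.9 to 2.3 points for assumed failure rates of 1% to 3% per year, or roughly 1.5 to 4 failures among 155 implants. The score requirement also removes event-free patients with shorter follow-up and acts downward, so the net bias may be positive, nil or negative: at true 0.90 it runs from +1.8 points with no loss to −1.0 at 40% loss. All rates are assumptions. Only the intermediate report is affected by the four-year limit. The rule also conflicts with the SAP's own analysis population and censoring rule, and these need to be reconciled.

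**What to change.** In the SAP section Report Timing of survivorship assessment, remove both the late-score entry requirement and the four-year limit on reoperated or revised patients for the 5-year analysis. Replace them with a statement to this effect: *the 5-year Kaplan-Meier and life-table analysis includes all enrolled, implanted subjects as defined in General Considerations; every qualifying event up to the 5-year data cut-off is counted, whether or not the subject has a later score; subjects without an event are censored at last follow-up.*

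Lifting the four-year limit alone is not enough. It restores the failures but still drops event-free patients without a late score, giving 0.889 against a true 0.90 at 20% loss.

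The cost is a short SAP edit. No new data are needed, because removals and surgical interventions are already captured on the adverse event and surgical intervention forms. The 5-year figure may turn out slightly less favourable.
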